3. OBJECTIVES

| Primary Objectives | Corresponding Primary Endpoint |
|---|--------------------------------|
| Phase 1b: To determine the safety and tolerability of neoadjuvant talimogene laherparepvec in combination with preoperative EBRT as assessed by incidence of dose-limiting toxicities (DLT) in subjects with locally advanced high grade soft tissue | Incidence of DLTs |

| | |
|--|---|
| sarcomas. | |
| Phase 2: To estimate the efficacy of neoadjuvant talimogene laherparepvec and radiotherapy as assessed by the pathological complete response rates (pCR) in subjects with histologically confirmed diagnosis of locally advanced STS that is unresectable with clear wide margins, for which preoperative radiotherapy is considered appropriate. | pCR rate - the proportion of subjects with pathologic tumor necrosis $\geq 90\%$ |
| Secondary Objectives Further assess the safety of talimogene laherparepvec given concurrently with preoperative external beam radiation in sarcoma patients. To estimate: 
• Overall response rate (ORR)• Time to progression (TTP)• Overall survival (OS) | Corresponding Secondary Endpoint Type, incidence, severity, and relatedness of AEs ORR – The proportion of subjects with a complete or partial response. TTP - Time from first day of study treatment to first documented disease progression Overall survival – Time from first day of study treatment to death due to any cause. |

For this study, pCR will be defined as $\geq 90\%$ tumor necrosis following concurrent radiation therapy and talimogene laherparepvec.

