Talimogene laherparepvec will be dosed at an initial dose of up to 4.0 mL of 10^6 PFU/mL on day 1 of week 1, followed by the target dose of up to 8.0 mL of 10^8 PFU/mL (Dose 0) three weeks later on day 1 of week 4, and dosed weekly until surgery. Initially 3 patients will be entered at the Dose 0 (following initial dose of up to 4.0 mL of 10^6 PFU/mL on day 1 of week 1) for talimogene laherparepvec and be monitored at this weekly dose through 4 injections, when safety issues will be addressed. Data from safety analysis will be reviewed with Amgen Medical and Safety team. If none or one of the 3 patients shows a DLT, three more patients will be entered into the study at this dose and be monitored at this weekly dose through 4 injections. If none or one of these 6 patients shows a DLT, this is the dose that will be used for the phase II relative efficacy assessment. Otherwise, talimogene laherparepvec dose will be deescalated and dose -1 will be explored as outlined below in Table 1. For this protocol DLT will be defined as an attributed adverse event (definite, probable or possible) that meets the criteria in Section 6.2.

Phase 2:

The phase 2 part of the study will provide an estimate of the relative treatment effect of talimogene laherparepvec in combination with preoperative EBRT in subjects with histologically confirmed diagnosis of locally advanced STS that is unresectable with clear wide margins, for which preoperative radiotherapy is considered appropriate, as measured by pathological response rates. Twenty- eight (28) patients will be enrolled into the phase 2 portion of this protocol.

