12. STATISTICAL CONSIDERATIONS

12.1 Study Design/Endpoints

Phase Ib

| Number of Patients with DLT at a Given Talimogene Laherparepvec Dose | Decision Rule |
|--|---|
| ≥ 2 | Dose level will be declared toxic. If this is the lowest dose level, stop the study due to excessive toxicity; otherwise enter three additional patients at the next lowest dose level. |
| ≤ 1 out of 3 | Enter three more patients at this dose level. |
| ≤ 1 out of 6 | This is the recommended Phase II dose. |

Up to 6 patients will be treated at each dose level. The recommended Phase II dose will be defined as the highest dose level for which at most 1 out of 6 patients experience a DLT.

Phase II

The primary objective of the Phase II portion of this study is to evaluate the preliminary evidence of anti-tumor activity of talimogene laherparepvec in combination with external beam radiation therapy. The primary endpoint of interest is pathologic complete response (pCR) rate defined as the proportion of subjects with pathologic tumor necrosis of $\geq 90\%$. Estimates of historic pCR based on tumor necrosis $\geq 90\%$ for the treatment of soft tissue sarcomas with external beam radiation therapy are not available in the current literature. However, a pCR rate of 30% would be considered unacceptable for the proposed combination treatment whereas a pCR of 55% or more is considered clinically important. Sample size requirements are based on an optimal Simon two-stage design with 80% power and a significance level of 5%. Nine (9) patients will

be enrolled in the first stage, and the study will be terminated if 3 or fewer respond. Otherwise, an additional 26 patients will be enrolled in the second stage. If 15 or more of the 34 total patients respond, the treatment will be deemed worthy of further investigation. This design has an expected sample size of 16.0 and a 0.73 probability of early termination.

Data Analysis and Reporting

The number and severity of all adverse events will be summarized by simple descriptive statistics. pCR and ORR (CR+PR) rate point estimates and 95% exact confidence intervals will be reported. For TTP (time from first day of study treatment to first documented disease progression) and OS (time from first day of study treatment to death due to any cause), survival curves using the Kaplan-Meier method will be constructed. Estimates along with 95% confidence intervals will be reported.

REFERENCES

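### The Phase II total is 28 in Section 5.1 and both 34 and 9 + 26 = 35 in Section 12.1; the stated optimal Simon design fits only 35

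*Combined protocol and SAP*

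**What the plan says.** Section 12.1 (Phase II) describes an optimal Simon two-stage design with 80% power and 5% significance. The rates to be separated are given as follows: "a pCR rate of 30% would be considered unacceptable for the proposed combination treatment whereas a pCR of 55% or more is considered clinically important".

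Nine patients are to "be enrolled in the first stage, and the study will be terminated if 3 or fewer respond". The text continues: "Otherwise, an additional 26 patients will be enrolled in the second stage". The final rule is: "If 15 or more of the 34 total patients respond, the treatment will be deemed worthy of further investigation". The stated properties are: "This design has an expected sample size of 16.0 and a 0.73 probability of early termination".

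Section 5.1 (Phase 2) gives a different enrolment figure: "Twenty- eight (28) patients will be enrolled into the phase 2 portion of this protocol".

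These are all complete sentences of current text. Some schema figures and pages are not available, but nothing readable links 28, 34 and 35.

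**The concern.** One single-arm cohort has three totals. The stage sizes and the denominator of the success rule disagree within one paragraph of Section 12.1, and both disagree with the enrolment target in Section 5.1.

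Staff who manage accrual may work from Section 5.1 while the statistician works from Section 12.1. Each would be following the protocol, and they would stop at different numbers. If enrolment ends at 28, the trial is 7 patients short of the total to which the cut-off of 15 belongs. The team would then either apply a cut-off too strict for the sample or choose a new one after stage 1. The trial is open-label, so pCR results could be known by then, and the primary decision rule would no longer be fully prespecified.

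**Working it through.** **Inputs.** All come from Section 12.1 except the last: p0 = 0.30, p1 = 0.55, alpha 5%, power 80%, n1 = 9, stop if 3 or fewer respond, n2 = 26, succeed at 15 or more, stated total 34, expected size 16.0, early termination 0.73. Section 5.1 gives 28. The plan does not say whether 5% is one- or two-sided; one-sided is assumed because it reproduces the stated design.

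**Formulas.** With X1 ~ Bin(n1, p) and X2 ~ Bin(N − n1, p):
- PET = P(X1 ≤ r1 | p0)
- EN = n1 + (1 − PET)(N − n1)
- P(success | p) = Σ over x > r1 of P(X1 = x) · P(X2 ≥ c − x). This is alpha at p0 and power at p1.

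**Step 1: reproduce the plan's figures.**
- PET = 0.0404 + 0.1556 + 0.2668 + 0.2668 = 0.7297, as stated (0.73).
- EN with 26 more patients: 9 + 0.2703 × 26 = 16.03, as stated (16.0).
- EN with 25 more patients (total 34): 9 + 0.2703 × 25 = 15.76, which is not 16.0.

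**Step 2: search for the optimal design.** An exhaustive exact-binomial search over totals from 10 to 49, with alpha ≤ 0.05 and power ≥ 0.80, gives the smallest EN at stop ≤ 3/9, success ≥ 15/35. This agrees with the stated 9, 3, 26, 15, 16.0 and 0.73. Only the 34 fails to match.

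**Step 3: the stated first stage (stop at ≤ 3/9) with each total.**

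| Total | Success if | Alpha | Power | EN at 30% |
|---|---|---|---|---|
| 35 | ≥ 15 | 0.0486 | 0.809 | 16.03 |
| 34 | ≥ 15 | 0.0397 | 0.798 | 15.76 |
| 34 | ≥ 14 | 0.0694 | 0.819 | 15.76 |
| 28 | ≥ 15 | 0.0068 | 0.591 | 14.14 |
| 28 | ≥ 13 | 0.0371 | 0.764 | 14.14 |
| 28 | ≥ 12 | 0.0700 | 0.804 | 14.14 |

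At 34 with the rule of 15, the loss is about one point of power. At 28, no cut-off meets both targets: 12 breaks the alpha limit, and 13 or more falls short on power.

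**Step 4: do other standard designs explain 28 or 34?**
- The minimax design has a total of 25.
- Reading 5% as two-sided (0.025 in one tail) gives an optimal design with total 34, but it is stop ≤ 4/12, success ≥ 16/34, EN 18.08. That contradicts the stated first stage, cut-off and EN.
- If stage 1 is changed, 28 can work: stop ≤ 3/10, success ≥ 13/28 gives alpha 0.042, power 0.811, PET 0.650, EN 16.31.
- So can 34: stop ≤ 2/7, success ≥ 15/34 gives alpha 0.042, power 0.805, EN 16.53.

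Neither of the last two is the design written in Section 12.1, and neither has the smallest EN.

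**The case against.** The strongest counter-argument is that 28 and 34 may not conflict. Section 12.1 allows up to 6 Phase Ib patients per dose level, and 28 + 6 = 34. If the 6 patients at the recommended dose count towards pCR, the only remaining error is one patient in the stage sizes. In support, Section 4.1 has one eligibility list for the whole study, the Phase 2 regimen in Section 5.1 follows that of Phase 1b, and Section 11.1 defines pCR for the study as a whole.

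This cannot be ruled out as the origin of 34, but it does not remove the problem. No readable passage says that Phase Ib patients count, and Section 5.1 places the 28 within the Phase 2 portion. Section 3 gives the phases separate primary objectives, and its Phase 1b objective refers to "incidence of dose-limiting toxicities (DLT) in subjects with locally advanced high grade soft tissue" sarcoma, a restriction absent from the Phase 2 objective. That wording difference is weak evidence by itself, given the shared eligibility list. More decisively, 9 + 26 is still not 34. If pooling was intended, it has to be written down.

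It can also be said that Section 12.1 governs and 28 is merely a leftover. That is plausible, but a reader of Section 5.1 has no means of knowing it.

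**Conclusion.** The inconsistency is real and should be fixed. The 34 is most simply read as a one-patient slip for 35, with negligible effect (power 0.798 against 0.809). The material conflict is 28 against 35. Applied at 28, the rule of 15 responses raises the chance of missing a true 55% pCR rate from 19% (1 − 0.809) to 41% (1 − 0.591).

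The conclusion rests on exact binomial calculation with the plan's own rates and targets and on a one-sided 5% level. Confidence is high that the totals conflict and that the stated design is the one with 35. The origin of 28 and 34 cannot be settled from the text. The design itself is recoverable, so this is a correction rather than a fundamental flaw.

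**What to change.** Choose one Phase II total, use it in both sections, and do so before any pCR results are known.

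- **(a) Keep the stated design (simplest).** In Section 12.1 change the denominator of the success rule from 34 to 35. In Section 5.1 replace 28 with up to 35 (9, then 26). Cost: a wording amendment, and up to 7 more patients than Section 5.1 states, but none beyond the 9 + 26 already in Section 12.1.
- **(b) Keep 28.** Restate the whole design in Section 12.1. For example: 10 patients in stage 1, stop if 3 or fewer respond, then 18 more, success if 13 or more of 28 respond (alpha 0.042, power 0.811, PET 0.650, EN 16.3). Remove the description as optimal. EN at a 30% pCR rate rises by about 0.3, and PET falls from 0.730 to 0.650. At a 55% rate, EN falls from 30.7 to 26.2, and the chance of wrongly stopping at stage 1 falls from 0.166 to 0.102. This option is open only if stage 1 has not already been judged at 3 of 9.
- **(c) Count Phase Ib patients.** If 28 meant new patients in addition to 6 Phase Ib patients at the recommended dose, say so in Section 12.1 and make the stage sizes add up to the stated total.

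Under (a) or (b), a sentence stating that Phase Ib patients do not count towards the Phase II total would remove the remaining ambiguity.

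### Does the planned 95% exact interval for pCR clash with the Simon success rule at 15 or 16 responders?

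*Combined protocol and SAP*

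**What the plan says.** Section 12.1 (Phase II) fixes the two reference rates: "a pCR rate of 30% would be considered unacceptable for the proposed combination treatment", "whereas a pCR of 55% or more is considered clinically important". The design basis is "Sample size requirements are based on an optimal Simon two-stage design with 80% power and a significance level of 5" per cent, and the document does not say whether that level is one-sided or two-sided. Nine patients enter the first stage, three or fewer responders stop the study, and otherwise 26 more are enrolled. The conclusion is tied to a count: "If 15 or more of the 34 total patients respond, the treatment will be deemed worthy of further investigation".

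The interval comes later in the same section, under Data Analysis and Reporting: "pCR and ORR (CR+PR) rate point estimates and 95% exact confidence intervals will be reported". The text names no particular exact method and makes no adjustment for the possible stop after nine patients. It attaches no consequence to whether the pCR interval contains 30%.

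**The concern.** A reader expects a test and an interval in the same section to agree. Here a report could announce that the treatment merits further study beside a 95% interval that contains the rate the protocol calls unacceptable. A sceptic might then discount a valid success. A team might choose a different interval after seeing the data. The disagreement has two sources. The main one is the level, 5% in one tail against 2.5% in each. The smaller one is that the ordinary interval ignores the stage-1 stop. One remedy would be to tie the decision to a two-stage exact p-value and a two-stage exact 90% interval, and keep the ordinary 95% interval as description.

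**Working it through.** **Inputs (Section 12.1).** Null rate 0.30, target 0.55, level 5%, power 80%, stop at 3 or fewer of 9, 26 further patients, success at 15 or more. The printed total is 34, but 9 + 26 = 35, so both are carried.

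**Reproducing the plan's figures.** Early termination at 30% is the sum over x = 0 to 3 of C(9,x) × 0.3^x × 0.7^(9−x) = 0.0404 + 0.1556 + 0.2668 + 0.2668 = 0.7297. Expected size is 9 + (1 − 0.7297) × 26 = 16.03. With 25 further patients (total 34) it would be 15.76. The plan states that "This design has an expected sample size of 16.0 and a 0.73 probability of early termination", so 35 is the total behind it.

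The chance of success at true rate p is the sum over x = 4 to 9 of P(X1 = x) × P(Bin(26, p) ≥ 15 − x).

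- Total 35: 0.0486 at p = 0.30 and 0.8095 at p = 0.55.
- Total 34: 0.0397 and 0.7979.

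**Is the 5% one-sided?** A search for the optimal design at one-sided 0.05 returns exactly this rule (3/9, then success above 14 of 35). At one-sided 0.025 it returns a different one (4/12, then success above 15 of 34, expected size 18.08). The stated level is therefore one-sided.

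**Intervals around the boundary.** The ordinary interval is Clopper-Pearson. The two-stage interval inverts the success probability above, with outcomes ordered by stage and then by responders. Entries are percentages.

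| Responders | Rule | Ordinary 95% | Ordinary 90% | Two-stage 90% | Two-stage p at 30% |
|---|---|---|---|---|---|
| 14/35 | not met | 23.9 to 57.9 | 26.1 to 55.3 | 28.0 to 65.6 | 0.0812 |
| 15/35 | met | 26.3 to 60.6 | 28.6 to 58.1 | 30.1 to 65.9 | 0.0486 |
| 16/35 | met | 28.8 to 63.4 | 31.2 to 60.8 | 32.4 to 66.4 | 0.0261 |
| 17/35 | met | 31.4 to 66.0 | 33.8 to 63.5 | 34.7 to 67.3 | 0.0125 |

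The ordinary 95% interval thus contains 30% at two counts that meet the rule. With 34 patients the same two counts are affected: 15/34 gives 27.2 to 62.1, 16/34 gives 29.8 to 64.9, and 17/34 gives 32.4 to 67.6.

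Neither change alone removes the disagreement at 15/35. The ordinary 90% interval starts at 28.6%, and a two-stage 95% interval starts at 27.7%.

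**How often (35 patients).** P(15) + P(16), and its share of all successes:

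- True rate 30%: 0.0225 + 0.0136 = 0.0361, which is 0.0361/0.0486 = 74% of successes.
- True rate 45%: 0.0793 + 0.0912 = 0.1705, or 34%.
- True rate 55%: 0.0291 + 0.0499 = 0.0790, and 0.0790/0.8095 = 10%.

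**Is the planned interval sound as an estimate?** Its coverage was enumerated over the two-stage design for true rates from 0.05 to 0.95. The lowest value is 94.6%, at a rate of 0.71.

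**What the alternative costs.** The upper limit of the two-stage 90% interval hardly moves: 65.5% for every count checked from 4 to 12 of 35, 65.6% at 14 and 65.9% at 15.

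- At 15/35 it spans 65.9 − 30.1 = 35.8 points, against 60.6 − 26.3 = 34.3 for the ordinary 95% interval.
- At 12/35, a clear failure, it is 24.1 to 65.5 and contains the 55% target. The ordinary 95% interval, 19.1 to 52.2, excludes it.
- At 5/35, an unlikely outcome, its lower limit of 16.9% lies above the observed 14.3%.

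**The case for a change.** The strongest case for a change is that the conflict falls where interpretation is most delicate. At a true rate of 45%, a third of successes would carry an interval that appears to contradict them, and at 30% nearly three quarters of false successes would. The two-stage 90% interval agrees with the rule on both sides of the boundary (28.0% at 14, 30.1% at 15). Writing it in would take a few sentences, and the choice is only credible if made before the data are seen. Section 12.1 has to be revisited anyway for its totals.

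The arithmetic stands, and so does the observation that the text omits the word one-sided. The inference from it does not. The plan already says what governs the conclusion, namely the number of responders, so there is no undecided choice between test and interval. The 74% share also cuts the other way: when the true rate is 30%, an interval that still reaches below 30% is a fair caution to the reader. The proposed remedy would leave the ordinary 95% interval in the report, so the awkward pairing would still be printed. It would also add a new one, a failed trial beside an interval that contains the target. Any benefit would come from labelling the intervals, and a label changes no result.

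**Conclusion.** The mismatch is real but calls for no change. A one-sided 5% screening rule and a two-sided 95% interval answer different questions: whether to go on, and how precisely the rate is known. The rule is valid at 35 patients (error 0.0486, power 0.81), and the interval performs close to its nominal level. They disagree at two counts only, with probability 3.6% at a true rate of 30%, 17% at 45% and 7.9% at 55%. No conclusion in the plan depends on the interval. The two-stage interval would trade one awkward reading for another, so it may be offered as a supplement but has no claim to replace the planned one. An analyst can recover the one-sided level from the stated expected size and early-termination probability.

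This rests on reading exact as Clopper-Pearson. At 16/35 the Wilson and Jeffreys lower limits (30.5% and 30.1%) would already exclude 30%, but at 15/35 those two intervals do not. It also rests on a total of 34 or 35. Section 5.1 gives 28 for phase 2. With 15 responders of 28, the single-stage one-sided tail at 30% is 0.0077, below 0.025, so the ordinary 95% interval would exclude 30% and the disagreement would not arise. Reconciling 28, 34 and 9 + 26 is a separate matter.

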APPENDIX A PERFORMANCE STATUS CRITERIA

| ECOG Performance Status Scale | | Karnofsky Performance Scale | |
|--------------------------------------|---|------------------------------------|--|
| Grade | Descriptions | Percent | Description |
| 0 | Normal activity. Fully active, able to carry on all pre-disease performance without restriction. | 100 | Normal, no complaints, no evidence of disease. |
| | | 90 | Able to carry on normal activity; minor signs or symptoms of disease. |
| 1 | Symptoms, but ambulatory. Restricted in physically strenuous activity, but ambulatory and able to carry out work of a light or sedentary nature (e.g., light housework, office work). | 80 | Normal activity with effort; some signs or symptoms of disease. |
| | | 70 | Cares for self, unable to carry on normal activity or to do active work. |
| 2 | In bed <50% of the time. Ambulatory and capable of all self-care, but unable to carry out any work activities. Up and about more than 50% of waking hours. | 60 | Requires occasional assistance, but is able to care for most of his/her needs. |
| | | 50 | Requires considerable assistance and frequent medical care. |
| 3 | In bed >50% of the time. Capable of only limited self-care, confined to bed or chair more than 50% of waking hours. | 40 | Disabled, requires special care and assistance. |
| | | 30 | Severely disabled, hospitalization indicated. Death not imminent. |
| 4 | 100% bedridden. Completely disabled. Cannot carry on any self-care. Totally confined to bed or chair. | 20 | Very sick, hospitalization indicated. Death not imminent. |
| | | 10 | Moribund, fatal processes progressing rapidly. |
| 5 | Dead. | 0 | Dead. |

NCI Protocol #:
Version Date: March, 13, 2023

APPENDIX B RECIST GUIDELINES

<http://www.eortc.be/recist/documents/RECISTGuidelines.pdf>

CONFIDENTIAL

NCI Protocol #:
Version Date: March, 13, 2023

APPENDIX C: CTCAE V.4.0

http://evs.nci.nih.gov/ftp1/CTCAE/CTCAE_4.03_2010-06-14_QuickReference_5x7.pdf

CONFIDENTIAL

APPENDIX D: CONTRAINDICATIONS AND ADVERSE EVENTS

CONTRAINDICATIONS

Talimogene laherparepvec is contraindicated in patients with a history of life-threatening hypersensitivity to talimogene laherparepvec or any of its excipients.

ADVERSE DRUG REACTIONS

Gastrointestinal disorders SOC:

Very Common ($\geq 10\%$)

- Nausea, Vomiting, Diarrhea, Constipation

Common ($\geq 1\%$ and $< 10\%$)

- Weight loss

General disorders and administrative site condition SOC:

Very Common ($\geq 10\%$)

- Chills, Pyrexia, Fatigue, Flu like symptoms, Injection site pain

Common ($\geq 1\%$ and $< 10\%$)

- Injection site reactions (including erythema, inflammation, warmth, pain [at injection site and at distant, non-injected lesions], swelling [at injection site and/or lymphadenopathy], or drainage may occur), Malaise

Metabolism and nutrition disorders SOC:

Common ($\geq 1\%$ and $< 10\%$)

- Dehydration

Blood and lymphatic system disorders SOC:

Common ($\geq 1\%$ and $< 10\%$)

- Anemia

Uncommon ($\geq 0.1\%$ and $< 1\%$)

- Plasmacytoma at the injection site

Musculoskeletal and Connective tissue disorders SOC:

Very Common ($\geq 10\%$)

- Myalgia, Arthralgia, Pain in extremity

Infections and Infestations SOC:

Common ($\geq 1\%$ and $< 10\%$)

- Cellulitis (see Warnings and Precautions), Oral herpes

Uncommon ($\geq 0.1\%$ and $< 1\%$)

- Delayed wound healing

Injury, poisoning and procedural complications:

Common ($\geq 1\%$ and $< 10\%$)

- Bruising

Vascular disorders SOC:

Common ($\geq 1\%$ and $< 10\%$)

- Flushing

Nervous System Disorder SOC:

Very Common ($\geq 10\%$)

- Headache

Common ($\geq 1\%$ and $< 10\%$)

- Dizziness

Skin and subcutaneous tissue disorders SOC:

Common ($\geq 1\%$ and $< 10\%$)

- Vitiligo

Respiratory, thoracic and mediastinal disorders SOC:

Uncommon ($\geq 0.1\%$ and $< 1\%$)

- Laryngeal swelling

EFFECTS ON ABILITY TO DRIVE AND USE MACHINES

None known.

OVERDOSE

The maximum dose of talimogene laherparepvec that can be safely administered has not been determined.

ABUSE AND DEPENDENCE

Talimogene laherparepvec is not a controlled substance. There is no evidence that talimogene laherparepvec is habit forming or could lead to dependence.

PEDIATRIC USE

No studies of talimogene laherparepvec have been conducted in pediatric subjects.

GERIATRIC USE

There are subjects > 65 as well as > 75 years of age who have received talimogene laherparepvec. However, no adequate and well-controlled studies have been designed to specifically evaluate the use of talimogene laherparepvec in geriatric subjects.

RENAL IMPAIRMENT

No clinical studies have been conducted in patients with severe renal impairment.

HEPATIC IMPAIRMENT

NCI Protocol #:
Version Date: March, 13, 2023

No clinical studies have been conducted in patients with severe hepatic impairment.

CONFIDENTIAL

